Aims: This randomized clinical trial (RCT) will test the feasibility, acceptability, and preliminary efficacy of a novel family-centered, psychoeducational intervention with known and newly identified factors to improve fertility preservation (FP) uptake, decision quality, and family communication among male adolescents and young adults (AYAs) newly diagnosed with cancer. The primary aim of this project is to examine preliminary efficacy of the psychoeducational intervention with regard to FP uptake.

Hypotheses: The primary hypothesis is that compared to standard of care control group (routine fertility consult at diagnosis, n=20), AYAs in the intervention arm (routine fertility consult at diagnosis + FP Decision Tool and Facilitated Conversation by trained interventionist; n=20) will have higher rates of FP uptake. The secondary hypotheses are that families in the intervention group will report better FP decision quality and report improvements in family communication, compared to those in the control arm.

Rationale: Nearly 9,000 males under age 20 are diagnosed with cancer in the U.S. each year¹. With 5-year survival rates exceeding 80%, the population of male childhood cancer survivors is now close to 200,000². Unfortunately, approximately 50% of male survivors have impaired fertility³⁻⁵, which can impede psychosexual development and diminish quality of life (QoL)⁶. Sperm banking is an established and effective method of FP for pubertal males⁷, yet only 25% of eligible adolescents bank sperm prior to

treatment⁸⁻¹². As these AYAs complete therapy and approach their reproductive years, many survivors and their parents *regret* missed opportunities for FP and report *distress* about potential infertility¹³⁻¹⁶.

Significant knowledge gaps exist with regard to pediatric FP:

- 1. Most research examining FP decisions has focused on females^{17,18}, despite a higher prevalence of cancer and treatment-related infertility in males¹⁹;
- 2. Many studies examining FP predictors have been conducted years after therapy and are subject to recall bias^{15,20};
- 3. Little attention has been paid to *decision quality* (satisfaction/regret) soon after FP decisions are made;
- 4. Although parents make most healthcare decisions even in late adolescence/young adulthood, *family factors* including parent-child communication about FP, have not been examined.

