- 3. *Many parents poorly estimate their sons/daughters' reproductive desires and worries, and struggle with separating their own desires from those of their children⁵².* A 2012 study in adolescent females recently diagnosed with cancer showed parents underestimated their daughters' reproductive concerns²⁸. Similarly, AYA males recently diagnosed with cancer ranked fertility in the top three life priorities, whereas parents were more concerned with their sons' health²⁷. Further, while many parents want to be grandparents in the future, they are often more willing to consider alternate means of family building (e.g. adoption) than their sons⁵³. Discordance, and/or parents' lack of awareness of their sons' reproductive goals and concerns, may ultimately lead to lower decision quality.
- 4. Notably, a recent study among 13-21-year old males within one week of initiation of cancer treatment demonstrated parents' recommendation to bank sperm, as compared with the medical

team, was the most robust predictor of a FP attempt^{26,49}. Thus, an intervention designed to increase caregiver-child communication should be examined within an established health behavior framework to examine its preliminary efficiency at increasing rates of FP in AYAs.

We completed an observational pilot study (IRB17-00883) testing feasibility and initial effects of a decision tool examining individual and family factors that impact FP decisions. The pilot informed the development of the decision tool that will be used in this study intervention, as well as the interviews used at the 1-month and 1-year follow-up. Recruitment rates were above 90% for visit 1, further demonstrating the feasibility of this type of study at the time of diagnosis.

4.0 **Study Endpoints**

The overarching goal of this project is to examine preliminary efficacy of the psychoeducational intervention in a pilot RCT. The *primary endpoint* is FP uptake following the intervention. The *secondary endpoints* are the Brief Subjective Decision Quality (BSDQ) questionnaire scores at 1-month and 1-year post-intervention and the change in Parent Adolescent Communication Scale (PACS) scores from baseline to 1-month and 1-year post-intervention.

5.0 **Study Intervention**

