This study seeks to improve FP in AYA males newly diagnosed with cancer by designing and evaluating the feasibility, acceptability, and preliminary efficacy of a family-centered psychoeducational intervention to optimize FP uptake and decision quality. To this effect, we will employ a blinded design. Both control and experimental groups will be pulled from one population (males with new cancer diagnoses) to control for biases and individual differences. Participants will be randomized and staff who consent families and conduct data collection activities will be blind to treatment group. The CBH Behavioral Trials Office (BTO) will maintain the randomization sequence and randomization to study group will be implemented through the data management software REDCap, which allows the randomization sequence generated by the statistician to be allocated via REDCap Randomization Module. In this module, the randomization sequence and group assignments are protected from the view of selected staff who use the REDCap program. Only BTO staff will have REDCap permissions to see the randomization sequence. Only the interventionist will have REDCap permissions to randomize and see the allocated group assignment when they log-on to REDCap. Outcome assessors (RAs) and investigators will be blinded to the intervention and will not have access to treatment allocation information in REDCap.

Baseline (Visit 1): At baseline (Visit 1), research staff will approach families in-person (at inpatient or outpatient clinic) or via phone, Webex, or email. Families (AYAs and parents) will receive a short briefing on the purpose of the study, provide informed consent, and staff will administer baseline measures after the family has consented to participate in the study. All measures will be completed by the child and both caregivers (when available). In the event that one family member is unable to participate or declines participation, the other family member(s) will be allowed to enroll separately. If a caregiver is only available remotely, a REDCap link to the survey will be provided electronically, and the caregiver will be included in the intervention remotely (e.g. via phone). If the entire family is only available remotely, participants will be contacted via phone and will be emailed a Webex link and REDCap links to participate in the study. The activities completed at Visit 1 are:

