- *Informed Consent:* Informed consent (and assent for participants 12-17 years of age) is obtained by study staff before data collection procedures or randomization. For adolescents between 12-17 years of age, informed consent will be obtained by a parent or legal guardian, and assent will be provided by the adolescent. Those who are between 18-25-years of age will provide informed consent for themselves to participate.
- *Demographics:* Research staff ask participants to answer questions about age, race, ethnicity, religion, education, income, whom they live with, and their relationship to their child. AYAs will be asked to answer an additional four questions about their communiation with their parents. These questions were taken from the Parent-Adolescent Communication Scale (PACS).
- *Randomization:* Families who consent to participate will be randomized (by the interventionist) to the control arm or intervention arm (family-centered psychoeducational intervention) after completing baseline measures. If the family is randomized to the control arm, the interventionist will inform the family that they were randomized to the control group and debrief the family. If the family is randomized to the intervention arm, the interventionist will inform the family that they are conduct the interventionist will inform the family that randomized to the treatment group and conduct the intervention immediately following randomization.

1-month Follow-up (Visit 2, Baseline + 1 to 2 months): At the 1-month follow-up (Visit 2) research staff will contact control and intervention families in-person (at inpatient or outpatient clinic) or via phone or email. Families (AYAs and parents) will be reminded about the study and be asked to complete follow-up activities. All measures will be completed by the child and both caregivers (when available). If the child and/or second caregiver did not complete Visit 1, they will be invited to complete Visit 2. The activities completed at Visit 2 include:

- *FP Decision Survey:* Participants will complete a brief survey about their FP decision. Items will include questions such as who participants talked to about their FP decision and who made the final decision regarding FP. Surveys will not be scored but questions will be used to guide analyses.

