- *Brief Subjective Decision Quality measure (BSDQ):* A six-item scale used to measure decision satisfaction and administered to AYA and both parents. Item will be scored into a composite decision satisfaction score (0-7).
- *The Parent-Adolescent Communication Scale (PACS):* A twenty-item scale used to measure perceived communication between AYA and parents will be administered to AYA and both parents. AYA will rate communication with both mother and father. Parents will only rate communication with son. Item scored into three scales: openness, problems, and a composite communication score.
- *Parenthood Goals Survey:* A sixteen-item survey used to examine parental and AYA views on parenthood. This survey is a modified version of the FP Decision Tool. This survey will be given to families in both the control and intervention group.
- *Feasibility and Acceptability Survey:* For the intervention group only, AYA and parents will fill out a twelve-item scale that will be used to assess satisfaction with the intervention structure and

content. The scale will include a final open-ended question asking for comments/suggestions about the intervention. The parent survey will include an additional item specific to how the intervention helped them help their child.

• *Brief Interview:* Study staff will also complete a brief, 15-minute semi-structured interview separately with each participant. The interview will focus on what participants discussed in relation to FP, how they made their decision, how they feel about their decision, and how they feel overall about their fertility counseling experience. The final question will give families the opportunity to share any additional thoughts. Interviews will take place away from other participants to allow each interviewee to speak freely. Interviews will be audio recorded and transcribed verbatim and coded for thematic content by trained research staff.

1-year Follow-up (Visit 3, Baseline + 1-year (+/- 1 month): At the 1-year follow-up (Visit 3) research staff will contact control and intervention families in-person (at inpatient or outpatient clinic) or via phone or email. Families (AYAs and parents) will be reminded about the study and research activities. All measures will be completed by the child and both caregivers (when available). The activities completed at Visit 3 include:

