Chi-squared and t-tests will be used to evaluate primary and secondary outcomes. A chi-square analyses will examine the primary outcome of FP uptake (Y/N) as a function of treatment group status An independent samples t-test will examine whether the secondary outcomes of decision quality (numerical score on the BSDQ and family communication (numerical score on the PACS and difference scores on the PACS for AYA and parents) change between 1-month and 1-year follow-ups. Pearson's r correlations will be run to see if FP uptake (Y/N) is related to decision quality or family communication.

The two groups (intervention and control) will be examined in an *exploratory* manner to assess potential differences in factors known to affect FP decisions such as demographics (e.g. age), urgency to start treatment, knowledge, provider recommendation, and parent recommendation, as well as novel factors such as quality of parent-child communication. We will also examine these baseline factors as covariates within an analysis of covariance to see if might have a substantial impact on our effect size estimates for the larger RCT.

Quality Control of Data: Internal quality management of study conduct, data collection, documentation and completion will be conducted, under the direction of the PI. Quality control (QC) procedures will be implemented as follows:

- Informed consent: Study staff will review both the documentation of the consenting process as well as a percentage of the completed consent documents. This review will evaluate compliance with GCP, accuracy, and completeness. Feedback will be provided to the study team to ensure proper consenting procedures are followed.
- Source documents and the electronic data: Some data will be initially captured on source documents and will ultimately be entered into the study database. Some data will be entered directly into an electronic data capture system. To ensure accuracy of data initially captured on source documents, site staff will compare a representative sample of source data against the database, targeting key data points in that review. Some data will be entered directly into study databases. Electronic databases will be programed to alter study staff and/or participants of out of range values and/or potential errors.

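### The PACS change scores planned in Sections 4.0 and 17.0 cannot be computed from the Section 6.0 schedule, which lists the full PACS at 1 month only

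*Combined protocol and SAP*

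**What the plan says.** Family communication is a secondary objective in Section 1.0. The secondary hypothesis in Section 2.0 is that intervention families will "report improvements in family communication, compared to those in the control arm". Section 4.0 turns this into an endpoint: "the change in Parent Adolescent Communication Scale (PACS) scores from baseline to 1-month and 1-year post-intervention".

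The Data Analysis Plan in Section 17.0 uses a different interval. It applies an independent-samples t-test to whether the "numerical score on the PACS and difference scores on the PACS for AYA and parents) change between 1-month and 1-year follow-ups".

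Section 6.0 sets out what is collected at each visit:

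- **Visit 1.** The list opens with "The activities completed at Visit 1 are" and contains consent, demographics and randomisation. Under demographics, "AYAs will be asked to answer an additional four questions about their communiation with their parents"; these are said to come from the PACS. No PACS questions are listed for caregivers.
- **Visit 2 (1 month).** The PACS is described as follows: "A twenty-item scale used to measure perceived communication between AYA and parents will be administered to AYA and both parents". It is scored for openness, problems and a composite. "AYA will rate communication with both mother and father", while parents rate communication with their son only.
- **Visit 3 (1 year).** The list has the BSDQ, the Parenthood Goals Survey and an interview. The PACS is absent.

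Late joining is allowed: "If the child and/or second caregiver did not complete Visit 1, they will be invited to complete Visit 2". The Data Collection Procedures paragraph says that the data described in Section 6.0 will be collected for all participants.

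**The concern.** A change score needs the same score from the same person at both ends of the interval. Section 4.0 needs the PACS at baseline, 1 month and 1 year, and Section 17.0 needs it at 1 month and 1 year. Section 6.0 lists the full scale once. Staff who follow Section 6.0 would not collect the data that the endpoint and the test require.

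Three things are at stake: the whole caregiver part of the endpoint, every PACS change to 1 year, and the Section 17.0 test of PACS change. The hypothesis of improvement would then rest mainly on one post-intervention score. Section 17.0 says that the pilot is meant to supply effect size estimates and that these feed a larger RCT. As listed, it would supply no caregiver change estimate and no 1-year PACS estimate.

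**Working it through.** **PACS items listed in Section 6.0, by respondent and visit**

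| Respondent | Visit 1 | Visit 2 | Visit 3 |
|---|---|---|---|
| AYA | 4 | 20 | 0 |
| Caregiver | 0 | 20 | 0 |

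Of the 2 × 3 = 6 cells, the full scale is in 2, four items are in 1, and 3 are empty.

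**Largest number of items common to both ends of each interval** (the smaller of the two cells)

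| Interval | Needed by | AYA | Caregiver |
|---|---|---|---|
| Baseline to 1 month | Section 4.0 | min(4, 20) = 4 | min(0, 20) = 0 |
| Baseline to 1 year | Section 4.0 | min(4, 0) = 0 | min(0, 0) = 0 |
| 1 month to 1 year | Section 17.0 | min(20, 0) = 0 | min(20, 0) = 0 |

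The defined scores need all 20 items at both ends.

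- Section 4.0: 2 respondents × 2 intervals = 4 changes. None can be computed on the defined scores; at most 1 can be formed on four items.
- Section 17.0: 2 respondents × 1 interval = 2 changes. None can be computed.

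The one partial change (AYA, baseline to 1 month) also requires that the four baseline items recur unchanged in the 20-item form and refer to the same parent. The documents do not show the items, and the plan defines no four-item score.

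**What remains: the 1-month comparison between arms**

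The plan's own figure comes first. Section 17.0 gives 80% power for d = .91 with 20 per group, two-sided alpha .05. Using the noncentral t with df = 2n − 2 = 38 and noncentrality d√(n/2) = 0.91 × √10 = 2.878, power is 80.1%, so the figure reproduces. Solving for exactly 80% gives d = 0.909. This applies to AYAs, 20 v 20.

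For caregivers, Section 12.0 gives 70. An even split is 35 v 35, with a detectable d of 0.68 if clustering is ignored. Two caregivers from one family are not independent. Assuming that each of the 40 families has one or two caregivers, 70 − 40 = 30 families have two and 10 have one. The weighted mean cluster size is (30 × 2² + 10 × 1²)/70 = 130/70 = 1.857, and the design effect is 1 + 0.857ρ. The documents give no within-family correlation ρ, so a range is shown:

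| Assumed ρ | Design effect | Effective n per arm | Detectable d |
|---|---|---|---|
| 0.3 | 1.257 | 35/1.257 = 27.8 | 0.77 |
| 0.5 | 1.429 | 35/1.429 = 24.5 | 0.82 |
| 0.7 | 1.600 | 35/1.600 = 21.9 | 0.87 |

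These figures ignore attrition. They show only what the surviving comparison can detect; the scheduling conflict does not depend on them.

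**The case against.** The strongest reply is that the visit lists may simply be incomplete.

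- The Visit 3 list is introduced by a word that allows further items.
- The Visit 1 paragraph says that the child and both caregivers complete all measures, although the list gives caregivers only demographics.
- Section 17.0 treats knowledge, recommendations and quality of parent-child communication as baseline factors, most of which have no listed Visit 1 survey.
- The data inventory in Section 17.0 includes the PACS for each participant.
- The statement that Section 6.0 data will be collected does not say that nothing else will be.

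This stands in part: an omission from the list is possible at Visit 3 and cannot be excluded at Visit 1. But none of these places assigns the PACS to Visit 1 or Visit 3, and the Visit 1 list is worded as complete. Adding the PACS at Visit 3 alone would still leave caregivers with no baseline and AYAs with four items.

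The difference scores in Section 17.0 may also mean AYA-parent discrepancy rather than change over time, and it is unclear how an independent-samples test fits a question about change. On either reading the sentence still needs a 1-year PACS.

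Finally, a randomised comparison at 1 month is valid without a baseline, and this is a pilot. Both points are right, and they limit how serious the problem is. They do not make the stated endpoint computable.

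**Conclusion.** The concern holds. Sections 4.0, 6.0 and 17.0 cannot all be followed. As scheduled, 0 of the 4 changes in the endpoint and 0 of the 2 in the analysis can be computed on the defined PACS scores, and at most one four-item AYA change is possible. Anyone who first joins at Visit 2 would have no PACS baseline at all, though chart data would exist.

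The conclusion rests on reading the visit lists as written; whether the data will in fact be missing depends on what staff collect. The damage is confined to one secondary endpoint and its test. The primary endpoint, the between-arm BSDQ comparisons and the 1-month between-arm PACS comparison stand. It should be fixed, but it does not threaten the trial's main result.

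**What to change.** Reconcile Sections 2.0, 4.0, 6.0 and 17.0 in one of two ways, deciding before outcome data are seen by arm.

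**(a) Fit the endpoint to the schedule.** Restate the hypothesis and endpoint as the 1-month PACS compared between arms. Use the AYA four-item baseline as a covariate in the AYA analysis (Section 17.0 already plans an exploratory analysis of covariance) and account for caregivers clustered in families. Delete the 1-year PACS endpoint and the test of change from 1 month to 1 year. The cost is a text amendment to Sections 2.0, 4.0 and 17.0, plus an update of the registered outcomes if registration has been made. No new data are collected. The price is a narrower endpoint with no caregiver baseline.

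**(b) Fit the schedule to the endpoint.** List the PACS at Visit 3. If change from baseline is wanted, give AYAs and caregivers the same PACS items at Visit 1 before randomisation, and state how those who join at Visit 2 are analysed. Make Section 17.0 test the intervals named in Section 4.0. With the full scale, each added visit costs 20 × 2 = 40 responses for an AYA rating two parents and 20 per caregiver. With four items it costs 4 × 2 = 8 and 4, assuming that the AYA rates each parent separately. Visit 1 falls at diagnosis, where Section 2.0 itself notes concern about burden. Families already past Visit 1 cannot be given a baseline.

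Under either option, use a four-item AYA change only if the Visit 1 items match the Visit 2 items in wording and in the parent rated.

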Intervention Description: The intervention will be administered by a trained interventionist who has participated in ENRICH/ECHO, an oncofertility communication training program. The interventionist will administer the digital FP Decision Tool to families in the intervention arm and will facilitate a guided discussion about responses and discrepancies. The FP Decision Tool asks 25 questions examining each AYA's thoughts or feelings regarding parenthood and fertility preservation. The parent version asks the same 25 question, plus an additional 9 questions asking the parent to rate their son's feelings on certain topics (i.e. whether their son wants to have a child, whether their son would be as happy with an adopted child versus a biological child). Items are coded based on the domains of the HBM (perceived benefits, perceived barriers, perceived threats, self-efficacy, and cues to action). The decision tool was developed using the HBM and is based on factors associated with FP uptake and decision quality in the literature, as well as new factors identified in the preliminary work of this research group.

AYAs and parents independently complete the electronic tool; an automated Quick View report is generated, highlighting misconceptions and parent-AYA discrepancies. The interventionist uses this information to facilitate a conversation with AYA and their caregiver(s). Specifically, the interventionist uses standardized prompts/language to: 1) address knowledge gaps/misconceptions, 2) share participants' fertility-related values and goals with one another*, 3) highlight discrepancies between responses*, and 4) promote family communication and consensus building. The facilitated conversation will be audio recorded.

Intervention Rationale: The intervention is designed to take participant's answers and provide a conversation tailored to their questions and needs. It will be carried out by one interventionist that has completed ENRICH/ECHO (oncofertility communication) training to ensure the intervention will not unnecessarily burden patients and families. Additionally, the intervention is designed to be short (less than 20 minutes). It is expected that participants will be present for the entire intervention in order to have their baseline data included in analyses.

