Data Collection Procedures: Data described in Section 6.0 will be collected for all participants. Data will be collected by trained research staff using an online survey tool (e.g., REDCap) or paper and pen questionnaires. Some data may be obtained from the participant's electronic medical record. Data collected at Visit 1 will be collected before the intervention begins, and data collected at Visits 2 and 3 will be collected after the intervention ends.

End of Study Definition: A participant is considered to have completed the study if they completed the baseline assessment, as well as the 1-month and 1-year follow-up assessments.

Lost-to-Follow-up Definition: A participant will be considered lost to follow-up if they fail to return for scheduled visits and study staff are unable to contact the participant after at least 3 attempts via phone or email.

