14.0 Withdrawal of Subjects*

Participants may be withdrawn if the intervention causes distress and it is determined by the interventionist and/or medical team that is not in the participant's best interest to continue. If the participant withdrawals from the intervention, study staff will encourage completion of study data collection, per intent-to-treat methodology.

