17.0 Data Management* and Confidentiality

Data Collection & Management: Data collection will be the responsibility of the study staff under the supervision of the PI. The PI will be responsible for ensuring the accuracy, completeness, legibility, and timeliness of the data reported.

All source documents will be completed in a neat, legible manner to ensure accurate interpretation of data. Hardcopies of the study visit worksheets will be provided for use as source document worksheets for recording data for each participant consented/enrolled in the study. Data recorded in the electronic case report form (eCRF) derived from source documents will be consistent with the data recorded on the source documents.

Clinical data (including AEs) and clinical laboratory data will be entered into secure study databases, if needed. The data system includes password protection and internal quality checks, such as automatic range checks, to identify data that appear inconsistent, incomplete, or inaccurate. Clinical data will be entered directly from the source documents.

Only authorized study staff will have access to study data.

Sample Size Determination: The sample was determined based on the medium-large effects found in our previous work and work by Klosky et al. and is sufficient to find similar sized effects; thus our proposed sample size will enable us to detect effect sizes previously found in the literature^{26,54-56}.

A sample size of n=20 per group will provide 80% power to detect large effect sizes of w=.45 for the chisquare analysis and d=.91 for the independent samples t-test. Because this is a pilot study, the focus will be on generating reliable effect size estimates for our primary outcome (FP uptake) comparing the intervention to standard care, rather than on statistical significance (using two-sided type I error rates (alpha values) of no more than .05). The proposed sample size is sufficient for gleaning this information.

Data Analysis Plan: Analyses will be conducted according to intent-to-treat methods, in which all randomized participants are included. Summary statistics will be calculated and qualitative methods used to evaluate the feasibility of recruiting and enrolling children.

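### Section 5.0 ties use of baseline data to attending the whole session, a condition only the intervention arm can fail; this contradicts the plan's intent-to-treat statements, but few analyses are touched

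*Combined protocol and SAP*

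**What the plan says.** Under Intervention Rationale in Section 5.0, after remarking that the session is short (under 20 minutes), the protocol states: "It is expected that participants will be present for the entire intervention in order to have their baseline data included in analyses".

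Section 6.0 fixes the order of events. Families are allocated "to the control arm or intervention arm (family-centered psychoeducational intervention) after completing baseline measures", and the Data Collection Procedures add: "Data collected at Visit 1 will be collected before the intervention begins". After allocation the arms diverge. Intervention families go straight into the session. For control families the interventionist is to "inform the family that they were randomized to the control group and debrief the family".

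Two other sections deal with who is analysed. The Data Analysis Plan in 17.0 says: "Analyses will be conducted according to intent-to-treat methods, in which all randomized participants are included". Section 14.0 says that when a participant withdraws from the intervention, "study staff will encourage completion of study data collection, per intent-to-treat methodology".

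Baseline data matter in two places. Section 4.0 names as a secondary endpoint "the change in Parent Adolescent Communication Scale (PACS) scores from baseline to 1-month and 1-year post-intervention". Section 17.0 adds an exploratory comparison of the arms on factors known to affect the decision, and an analysis of covariance with baseline factors as covariates.

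**The concern.** Read literally, the 5.0 sentence makes inclusion of baseline data conditional on something that happens after randomisation. Only one arm can fail the condition. A control participant has no session to leave, so a control's baseline data are always kept. An intervention participant who leaves early would lose data that were complete and valid before allocation was known.

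Any comparison using those data would then set selected intervention participants against all controls, and would no longer compare the groups as randomised. A covariate-adjusted model fitted to complete records would also rest on different people from the unadjusted estimate. In 17.0 the adjusted analysis is an exploratory check on whether baseline factors might materially alter the effect-size estimates carried to the larger trial. That check is harder to interpret if the set of participants changes along with the covariates.

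**Working it through.** The point turns on the text, and no figure in the plan needs reproducing for it.

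**Step 1: is the condition post-randomisation and one-sided?** Section 6.0 puts baseline measures before randomisation and the session immediately after it, in the intervention arm only. So yes on both counts.

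**Step 2: does another section resolve it?** Sections 14.0 and 17.0 state intent-to-treat without exception. No section defines a per-protocol set or confines the 5.0 condition to one. The two statements stand unreconciled.

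**Step 3: which analyses use the affected data?** The measures listed in 6.0 for each visit give the reach.

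| Analysis | Data needed | Affected? |
|---|---|---|
| Primary: uptake by arm, chi-square (17.0) | Uptake yes/no | No |
| Decision quality (BSDQ) at 1 month and 1 year | Visits 2 and 3 only | No |
| t-test as worded in 17.0 (change between 1 month and 1 year) | Visits 2 and 3 only | No |
| Change in communication (PACS), baseline to 1 month (4.0) | Visit 1 has four PACS items, for AYAs only; Visit 2 has the twenty-item scale | Yes, for the four AYA items |
| Change in communication, baseline to 1 year (4.0) | The Visit 3 list has no PACS | Not computable on the listed schedule |
| Exploratory arm comparison and covariance analysis (17.0) | Mixed sources | Only where Visit 1 survey demographics or the four items are used |

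On the last row, 17.0 names demographics, urgency to start treatment, knowledge, provider recommendation, parent recommendation and parent-child communication. Of these, the Visit 1 list shows only demographics and the four communication items. Date of birth is also held in the tracking sheet, so age does not depend on the survey. Chart-review items are not participant baseline measures and would not be lost.

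**Step 4: size.** Suppose k of 20 intervention AYAs leave early. Let S be the mean score of stayers and L that of leavers, in SD units.

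- Mean of all randomised = [(20 − k)S + kL]/20
- Mean if leavers are dropped = S
- Shift = S − [(20 − k)S + kL]/20 = (k/20)(S − L)

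The documents supply neither k nor S − L. As an assumed range, take k from 0 to 3 and a stayer-leaver gap of 0 to 1.0 SD in either direction:

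- k = 0: no shift
- k = 1: 0 to (1/20)(1.0) = 0.05 SD
- k = 2: 0 to (2/20)(1.0) = 0.10 SD
- k = 3: 0 to (3/20)(1.0) = 0.15 SD

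For scale, the 95% confidence half-width for a difference in means with 20 per arm is t(0.975, 38 df) × √(2/20) = 0.64 SD. The largest shift shown is 0.15/0.64 = 0.23 of that. This is an illustration and not an estimate.

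**The case against.** The strongest reply is that the sentence is not an analysis rule. It sits in rationale text, is phrased as an expectation, and names no analysis set or exclusion procedure. An analyst working from 17.0 would exclude nobody, and 14.0 already covers the person who stops the intervention. This stands in part: nothing shows that the condition would be applied, so the concern is conditional. It does not remove the contradiction, because the sentence states a consequence for the analyses and no other section withdraws it.

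A second reply is that baseline data here may mean the decision-tool answers. Those exist only in the intervention arm, so no between-arm comparison would be touched. The same paragraph does speak of the intervention taking participants' answers, and 17.0 lists decision-tool responses among the study data, so the reading is possible. It is less natural, because the tool is part of the intervention while 6.0 places Visit 1 data before it. Having to choose between the readings is itself a reason to clarify.

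A reader might also infer that the trial's intent-to-treat analysis as a whole, or its primary result, is compromised. The documents do not support that. The sentence concerns baseline data only, and the primary chi-square uses none. Nor do they support harm to a 1-year communication change or to the planned t-test. The Visit 3 list has no PACS, and 17.0 specifies no test of change from baseline.

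**Conclusion.** Wrong as written (an internal contradiction), and minor. Section 5.0 sets a one-sided, post-randomisation condition on baseline data that 14.0 and 17.0 do not allow. What could be lost is limited to Visit 1 survey demographics and four AYA communication items. The effect on the primary analysis and on decision quality is nil. Elsewhere the size and direction of bias cannot be known, since no early-leaving rate is given; with a session under 20 minutes the effect may well be small, or zero if nobody leaves. The conclusion assumes that baseline data means Visit 1 measures, that the visit lists in 6.0 are complete, and that the sentence might be followed.

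**What to change.** Delete the sentence in 5.0, or confine it to a named per-protocol or fidelity sensitivity analysis. Add to 17.0 a statement that every randomised participant is analysed in the assigned arm with all baseline data collected, whether or not the session was completed.

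The cost is one sentence removed and one added, with no new data. If the sponsor keeps the condition for a sensitivity analysis, presence must be recorded at every session; the fidelity review in 5.0 covers only a random selection of recordings and would not be enough. Keeping early leavers may dilute the estimated effect slightly, which is what the plan's own intent-to-treat principle accepts. The change should be made before analysis so that the choice cannot depend on the data.
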